3. OBJECTIVES AND OUTCOME MEASURES/ENDPOINTS

The primary objective of the SOPHIST trial is to investigate the effect of 16-week treatment with sotagliflozin in addition to standard of care on QoL compared to placebo in participants with type 1 diabetes and HF symptoms.

3.1. CMR sub-study objectives

The primary objective of the CMR sub-study is to investigate the effect of 16 weeks treatment with sotagliflozin in addition to standard of care on myocardial blood flow compared to placebo in individuals with HF and type 1 diabetes.

3.2. Table of endpoints/outcomes

Primary Objective		
Objectives	Outcome Measures	Timepoint(s)
To investigate the effect of sotagliflozin 200mg once daily in addition to standard of care on quality of life	Change from baseline in KCCQ clinical summary score	Weeks 0 and 16

Secondary Objectives		
Objectives	Outcome Measures	Timepoint(s)
To investigate the effect of sotagliflozin 200mg once daily in addition to standard of care on QoL	Change from baseline in KCCQ clinical summary score	Weeks 0 and 4
	Change from baseline in KCCQ overall summary score	Weeks 0, 4 and 16
	Proportion of participants with a ≥ 5 , ≥ 10 and ≥ 15 point increase in KCCQ clinical and overall summary scores	Weeks 0 and 16
	Change from baseline in Diabetes Treatment Satisfaction Questionnaire (DTSQs and DTSQc)	Weeks 0 and 16
	Change from baseline in EQ-5D-5L score	Weeks 0 and 16
To investigate the effect of sotagliflozin 200mg once daily in addition to standard of care on walking distance	Change from baseline in distance covered during 6-minute walk test	Weeks 0 and 16
To investigate the effect of sotagliflozin 200mg once daily in addition to standard of care on NT-proBNP	Change from baseline in NT-proBNP	Weeks 0 and 16
To investigate the effect of sotagliflozin 200mg once daily in addition to standard of care on glycaemic control	Change from screening in HbA1c	Screening and week 16

To provide information on safety and tolerability of sotagliflozin 200mg once daily in addition to standard of care compared to placebo	Proportion of participants with level 2 or level 3 hypoglycaemia	Week 0 to weeks 16 and 20
	Proportion of participants with DKA	Week 0 to weeks 16 and 20
	Proportion of participants requiring hospitalisation due to HF	

Exploratory Objectives		
Objectives	Outcome Measures	Timepoint(s)
To investigate the effect of sotagliflozin 200mg once daily in addition to standard of care on HF symptoms, signs and clinical outcomes	Change from screening in New York Heart Association (NYHA) class	Screening, weeks 16 and 20
	Change from baseline in daily loop diuretic dose	Weeks 0 and 16
	Change from baseline in systolic and diastolic blood pressure.	Weeks 0 and 16
	Number of hospitalizations and deaths (first and total number) due to heart failure	Week 0 to weeks 16 and 20
To investigate the effect of sotagliflozin 200mg once daily in addition to standard of care on renal parameters	Change from baseline in eGFR, serum creatinine, urine albumin to creatinine ratio	Weeks 0 and 16
To investigate the effect of sotagliflozin 200mg once daily in addition to standard of care on diabetes-related parameters	Change from baseline in total, basal and bolus insulin doses.	Weeks 0, 4 and 16
	Change from baseline in body weight.	Weeks 0 and 16
To investigate the effect of sotagliflozin 200mg once daily in addition to standard of care on Continuous Glucose Monitor (CGM) metrics recommended by the international consensus on the use of CGM ³⁸	Mean blood glucose level over preceding 14 days	Weeks 0, 4 and 16
	Blood glucose percentage time in range (3.9-10.0 mmol/L) over preceding 14 days	Weeks 0, 4 and 16
	Blood glucose percentage time below range (3.0-3.8 mmol/L and <3.0 mmol/L) over preceding 14 days	Weeks 0, 4 and 16
	Blood glucose percentage time above range (10.1-13.9mmol/L and >13.9 mmol/L) over preceding 14 days	Weeks 0, 4 and 16
	Glycaemic variability index	Weeks 0, 4 and 16

To investigate if trial outcomes are associated with baseline c-peptide levels	C-peptide level at baseline	Week 0
To investigate the effect of sotagliflozin 200mg once daily in addition to standard of care on ketone levels	Proportion of participants with non-acidotic ketosis (blood ketones >1.5mmol/L, blood pH of \geq 7.3, bicarbonate \geq 18mmol/l)	Weeks 0 and 16

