Blood samples: Collected, processed, and stored as per laboratory manual. Full blood count, urea and electrolytes, liver function tests, glucose and HbA1c will be analysed by the local NHS laboratory. Screening NT-proBNP (or BNP depending on local laboratory availability) will be performed in the local NHS laboratory, if a result is not available within 12 months of screening. NT-proBNP at baseline and week 16 and C-peptide at baseline will be stored frozen and shipped to Dundee for analysis for trial outcomes. Additional optional blood samples at baseline and 16 weeks will be collected for future biomarker research dependent on participants consent, see section 7.2.1. A maximum of 60 ml of blood will be obtained at any visit.

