Participants with type 1 diabetes should be aware of diabetic ketoacidosis. Further information on how to prevent, recognise, and treat DKA will be provided along with educational prompts. Participants will be also educated about precipitating factors for DKA (e.g. acute medical illness, vomiting, insulin pump failure, excessive carbohydrate restriction, excessive alcohol), when to discontinue therapy if these events occur and will be provided with contact details of the local research team and relevant emergency contacts for advice should any of these situations occur.

In addition to the above monitoring, participants will be advised to perform additional ketone testing if capillary/CGM glucose is >11.1 mmol/L for >2 hours or if feeling sick, according to standard sick day rules for diabetes management. Participants will be advised to check blood ketones if feeling unwell even when the capillary glucose levels are not particularly high, or with changes in diet, activity, insulin dose or events known to precipitate ketoacidosis and follow sick day rules as discussed with local team. If blood ketones are ≥ 0.6 mmol/L the clinician and participant will be encouraged to document reasons (e.g., alcohol, recent illness) for this and how it was managed. Advice will also be given regarding other times to check ketone levels (e.g., guidance is also given in Appendix 6 STOP-DKA protocol)⁴¹. Participants may be given a copy of the STOP-DKA guidelines, or local guidelines, dependent on local investigator's preference.

In summary the following strategies will be used to minimise DKA risk in addition to the educational measures:

- Participants will be asked to perform capillary ketone testing 4 times per day, 3 days before and 3 days after initiation of active drug/placebo, and 2 hours after changing each insulin giving set for those on insulin pump therapy as described earlier.
- Risk mitigation strategies, e.g. following the STOP-DKA Protocol if feeling sick or unwell with symptoms suggestive of impending DKA.

DKA will be defined as: blood ketone >3.0 mmol/l **and** blood pH of <7.3 or a bicarbonate <18 mmol/l.

Hypoglycaemia:

Hypoglycaemic events during the trial will be defined and documented as the following:

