16.4. Appendix 4 – Schedule of Procedures

	Visit 1 (Screening)	Visit 2	Visit 3 (Baseline)	Visit 4	Visit 5	Visit 6	Visit 7	Visit 8
	-30 days to -14 days	-7 days +/- 3 days	Day 0	Week 1 +/- 3 days	Week 4 +/- 3 days	Week 10 +/- 3 days	Week 16 +/- 3 days	Week 20 +/-3 days
	Research Site	Remote/ Research Site	Research Site	Remote/ Research Site	Research Site	Remote/ Research Site	Research Site	Remote/ Research Site
Informed Consent	X							
Eligibility	X		X					
Demographics	X							
Medical History	X							
NYHA Class	X						X	X
Record Concomitant Medications	X	X	X	X	X	X	X	X
Adverse Events		X	X	X	X	X	X	X
Weight	X		X				X	
Height, Waist and hip circumference	X							
Blood Pressure & pulse	X		X				X	
Physical Examination	X						X	
ECG	X							
Echocardiography, if required		X						
Review of Glucose Management including ketone check		X	X	X	X	X	X	X
Education for glucose and ketone management		X	X	X	X	X	X	X
Registration with app such as LibreView/Clarity etc. (if not already signed up), optional		X						
Documentation of summary Data and/or glucose readings from CGM, from previous 2 weeks			X		X		X	
Documentation of glucose and ketone readings		X	X	X	X	X	X	X
Documentation of hypoglycaemic and DKA events		X	X	X	X	X	X	X

	Visit 1 (Screening)	Visit 2	Visit 3 (Baseline)	Visit 4	Visit 5	Visit 6	Visit 7	Visit 8
	-30 days to -14 days	-7 days +/- 3 days	Day 0	Week 1 +/- 3 days	Week 4 +/- 3 days	Week 10 +/- 3 days	Week 16 +/- 3 days	Week 20 +/-3 days
	Research Site	Remote/ Research Site	Research Site	Remote/ Research Site	Research Site	Remote/ Research Site	Research Site	Remote/ Research Site
KCCQ	X		X		X		X	
DTSQ (status at baseline, change and status at 16 weeks)			X				X	
EQ-5D-5L			X				X	
6 minute-walk test			X				X	
Urine pregnancy test	X		X					
Safety Bloods (FBC, U&E, LFT, glucose)	X		X		X		X	
HbA1c	X						X	
NT-proBNP or BNP (local) if required	X							
NTproBNP for central lab analysis (Dundee)			X				X	
C-peptide for central lab analysis (Dundee)			X					
Urine albumin, creatinine, sodium			X		X		X	
Additional research bloods			X				X	
Additional research urine samples			X				X	
Randomisation			X					
Dispensing of IMP*			X					
Compliance to IMP				X	X	X	X	
IMP Accountability			X				X	

	Visit 1 (Screening)	Visit 2	Visit 3 (Baseline)	Visit 4	Visit 5	Visit 6	Visit 7	Visit 8
	-30 days to -14 days	-7 days +/- 3 days	Day 0	Week 1 +/- 3 days	Week 4 +/- 3 days	Week 10 +/- 3 days	Week 16 +/- 3 days	Week 20 +/-3 days

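### The exploratory outcome of non-acidotic ketosis cannot be confirmed as defined, because it needs blood pH and bicarbonate and no visit schedules a pH

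*Protocol*

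**What the plan says.** The last exploratory row of the table in section 3.2 serves an objective on the effect of sotagliflozin "in addition to standard of care on ketone levels". Its measure is "Proportion of participants with non-acidotic ketosis (blood ketones >1.5mmol/L, blood pH of" 7.3 or above, and bicarbonate 18 mmol/L or above. The timepoint column gives weeks 0 and 16.

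The blood tests are described in two places. Appendix 4 has one safety row, "Safety Bloods (FBC, U&E, LFT, glucose"), at Visits 1, 3, 5 and 7. Section 7.7 says "Full blood count, urea and electrolytes, liver function tests, glucose and HbA1c will be analysed by the local NHS laboratory". Appendix 4 also has a ketone check, and a row headed "Documentation of glucose and ketone readings", at each of Visits 2 to 8.

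Section 7.8 gives the neighbouring definition: "DKA will be defined as: blood ketone >3.0 mmol/l" together with "blood pH of <7.3 or a bicarbonate <18 mmol/l". In section 3.2 the DKA outcome is counted over "Week 0 to weeks 16 and 20".

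**The concern.** The outcome is a conjunction of three measurements, and the plan collects only the first of them for certain. When a ketone reading exceeds 1.5 mmol/L, the protocol gives no scheduled means of showing that pH and bicarbonate were normal. The result is either a comparison that is nearly empty in both arms, or one driven by which participants happened to have a blood gas taken for clinical reasons.

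The timing adds to this. Randomisation and dispensing take place at Visit 3, so a week 0 value is a baseline value. Only week 16 can reflect treatment.

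The two definitions also leave a space between them. DKA needs ketones above 3.0 mmol/L with acidosis, while this outcome needs ketones above 1.5 mmol/L without acidosis. Acidosis at ketones above 1.5 and up to 3.0 mmol/L belongs to neither.

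Section 2.1 puts DKA first among the identified risks. An exploratory ketone outcome is a natural supporting measure, but only if it can be derived.

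**Working it through.** The protocol states no figure to reproduce here. The check sets the definition against the data collection, and then the two definitions against each other.

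**Step 1. Components against the schedule** (section 3.2 against Appendix 4 and section 7.7)

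| Component needed | Scheduled collection |
|---|---|
| Ketones >1.5 mmol/L | Ketone check and readings at Visits 2 to 8 |
| pH ≥7.3 | 0 of 8 visits |
| Bicarbonate ≥18 mmol/L | Named at 0 of 8 visits |

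Section 7 says that all procedures follow Appendix 4. Some laboratories may report bicarbonate with urea and electrolytes; the protocol does not say so, and the laboratory manual is not shown. Even if they do, pH is still missing.

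**Step 2. Who can be classified.** All three conditions must hold for a case.
- Ketones 1.5 mmol/L or below: definitely not a case, and no blood gas is needed.
- Ketones above 1.5 mmol/L: cannot be confirmed as a case without pH and bicarbonate.

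So non-cases can be identified and cases cannot.

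**Step 3. Does another reading of the timing rescue it?** The timepoint column is not used uniformly. Insulin doses at visits cover the 7 days before (section 7.8), and the CGM rows cover the preceding 14 days.
- Values on the visit day: no pH is scheduled.
- A look-back before each visit: home ketone readings carry no pH.
- Cumulative from week 0 to week 16: pH exists only where someone was tested clinically, so home readings above 1.5 mmol/L without a blood gas stay unresolved.

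The outcome fails under all three.

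**Step 4. The space between the two definitions.** Both were applied to a grid of ketones (0.5, 1.5, 1.6, 2.5, 3.0, 3.1, 5.0), pH (7.2, 7.3, 7.4) and bicarbonate (15, 17.9, 18, 24), which is 7 × 3 × 4 = 84 cells. Of the 12 pH and bicarbonate pairs, 2 × 2 = 4 are non-acidotic and 8 are acidotic. Three ketone values lie above 1.5 and up to 3.0, so there are 3 × 8 = 24 acidotic cells in that band.

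The DKA sentence can be grouped in two ways.
- Ketones >3.0 and (pH <7.3 or bicarbonate <18): 24 of the 24 cells meet neither definition.
- (Ketones >3.0 and pH <7.3) or bicarbonate <18: the cells left out have pH 7.2 with bicarbonate 18 or 24, which is 3 × 2 = 6.

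No cell meets both definitions under either grouping. The gap narrows under the second but does not close. These counts show where the gap lies; they are not frequencies of events.

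**Step 5. Where an event in the gap would go.** Under section 9.2, worsening glycaemic control is treated as an outcome and not as an adverse event, except that events leading to hospitalisation or death are recorded as SAEs. The adjudication committee reviews DKA and severe hypoglycaemia only. An event in the gap without hospitalisation therefore has no row in the DKA or ketosis outcomes.

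**The case against.** The strongest reply is that this is one exploratory row under an objective on ketone levels. The safety and tolerability block of section 3.2 holds hypoglycaemia, DKA and heart failure hospitalisation, and DKA is counted cumulatively there. That is correct and limits the weight of the point.

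The protocol also never says that DKA and non-acidotic ketosis are meant to cover every event, so an intermediate zone is not in itself a contradiction. That stands too. The gap is worth closing while the row is being rewritten, but the unscheduled pH is the main defect.

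It might be said that the SAP would settle this. A SAP can redefine the outcome; it cannot supply a pH that was not measured.

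A reader might go further than the documents allow in four ways:
- *That nobody can be classified.* Participants with ketones at or below 1.5 mmol/L are definite non-cases.
- *That acidotic events in the gap vanish from the trial.* Hospitalised or fatal ones are SAEs, a medically significant laboratory abnormality may be reported as an adverse event (section 9.2), and ketone readings are documented at Visits 2 to 8.
- *That the outcome is proven to look at two calendar days only.* The timepoint column is ambiguous, as step 3 shows.
- *That the number of lost events can be estimated from the DKA incidence in section 2.1.* That figure says nothing about how often acidosis occurs at ketones of 1.5 to 3.0 mmol/L, and no document gives such a rate. A bias in the comparison between arms is likewise not shown.

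**Conclusion.** The point holds. As written, non-acidotic ketosis cannot be confirmed in any participant from scheduled data, because pH is scheduled at none of the eight visits. One of the two stated timepoints is before treatment. Separately, acidotic events with ketones above 1.5 and up to 3.0 mmol/L fall outside both ketone-related outcomes, wholly or in part depending on how the DKA sentence is grouped.

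The consequence is limited to an exploratory comparison that is likely to be nearly empty, and to incomplete reporting of ketone-related events that do not lead to hospitalisation or death. The number of participants affected cannot be calculated from the protocol. The conclusion assumes that the laboratory manual adds no routine blood gas to the schedule.

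**What to change.** Reconcile section 3.2 (the ketosis and DKA rows), section 7.8 and Appendix 4 as follows:

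1. Define the outcome as the proportion of participants with any documented blood ketone above 1.5 mmol/L not adjudicated as DKA, from first dose to weeks 16 and 20, using the readings already documented at Visits 4 to 8.
2. Within it, report as a listed subset any such event with measured pH below 7.3 or bicarbonate below 18 mmol/L. This is a subset, not a separate class. A participant with ketosis on one occasion and DKA on another counts in both outcomes.
3. Report the number of ketone readings per arm beside the result.
4. Leave the DKA definition unchanged. Because the new outcome excludes what was adjudicated as DKA, it does not depend on how that sentence is grouped.

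The cost is one rewritten row of the endpoint table and a line or two in the reporting tables, with no new procedure. There are two downsides to state. Where no blood gas was taken, absence of acidosis is unproven, so the label non-acidotic no longer fits. Testing frequency also differs between participants: section 7.8 asks for paired checks four times a day in the 3 days before and after starting, then at least weekly and when unwell, and continuous ketone monitors may be available to some. More testing finds more readings above the threshold, which is why item 3 is needed.

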3.3. Table of endpoints/outcomes (CMR sub-study)

Primary Objective		
Objectives	Outcome Measures	Timepoint(s)
To investigate the effect of sotagliflozin 200mg once daily in addition to standard of care on myocardial blood flow compared to placebo.	Change in global stress myocardial blood flow (mL/g/min) (measured using CMR)	Weeks 0 and 16
Secondary Objectives		
Objectives	Outcome Measures	Timepoint(s)
To investigate the effect of sotagliflozin 200mg once daily in addition to standard of care on myocardial blood flow and cardiac structure compared to placebo.	Change in global myocardial perfusion reserve index (units)	Weeks 0 and 16
	Change in global myocardial rest blood flow (mL/g/min)	Weeks 0 and 16
	Change in extracellular volume fraction (%)	Weeks 0 and 16
Exploratory Objectives		
Objectives	Outcome Measures	Timepoint(s)
To investigate the effect of sotagliflozin 200mg once daily in addition to standard of care on cardiac function compared to placebo.	Change in left ventricular ejection fraction (%)	Weeks 0 and 16
	Change in left atrial volume (mL/m ²)	Weeks 0 and 16
To evaluate whether changes in myocardial blood flow mediate or influence changes in main trial outcomes (as defined in Section 3.2).	Analyses will assess changes in myocardial blood flow and associations with changes in all main trial outcomes (Section 3.2).	Weeks 0 and 16

4. TRIAL DESIGN

A multi-centre, parallel-group, double-blind randomised controlled trial of sotagliflozin 200mg versus placebo, once daily in addition to standard of care in 320 adults with type 1 diabetes and HF in the UK. After receiving informed consent participants will be randomised in a 1:1 allocation to 16 weeks of oral sotagliflozin 200mg or matched placebo, once daily in addition to their standard care. Both the participants and investigators will be blinded to treatment allocation.

4.1. CMR sub-study design

A subset of participants (n=44) enrolled in the main SOPHIST trial will be invited to participate in a CMR sub-study at selected sites (including Dundee - the lead site for main trial and sub-study). Participants in the CMR sub-study will undergo CMR scans at baseline and after 16 weeks of treatment in addition to the standard trial assessments. CMR is intended to reflect the pre-treatment state and the effects of treatment in the preceding weeks.

5. TRIAL SETTING

Participants will be identified and recruited through NHS secondary care services. Potential participants may also be identified from the databases of the NHS Research Scotland Diabetes Network, Diabetes Research Register and the Scottish Health Research Register & Biobank (SHARE), Clinical Research Networks and local research registries. Where sites wish, primary care or patient identification centres may also be used.

The research activities will take place in approximately 12-15 secondary care settings within NHS trusts across the UK with the potential to include more sites depending on recruitment needs.

6. PARTICIPANT ELIGIBILITY CRITERIA

Patients are potentially eligible for SOPHIST if they have either a previous confirmed diagnosis of heart failure or undiagnosed heart failure. In recognition of this, we have included criteria to help identify those at higher risk of having undiagnosed heart failure who could be invited for screening:

6.1. For Screening visit

6.1.1. Eligibility

1. Age 18 years to <85 years.
2. Type 1 diabetes.
3. Meets the NTproBNP or echocardiographic randomisation inclusion criteria below

OR

Any of the following:

- Type 1 diabetes for >25 years **and** >40 years old

or

- History of any cardiac disease, for example but not limited to:
 - Hypertension, cardiac arrhythmia, myocardial infarction, angina, hyperlipidaemia

or

- History of any vascular disease, for example but not limited to:
 - Stroke, transient ischaemic attack, peripheral vascular disease, diabetic foot disease, vascular ulcer
- or**
- History of diabetic retinopathy
- or**
- History of renal disease, for example but not limited to:
 - Microalbuminuria (urine albumin/creatinine ratio ≥ 3 mg/mmol)
- or**
- Taking medications for any of the above, for example but not limited to:
 - Angiotensin converting enzyme inhibitors (ACE), angiotensin receptor blockers (ARB), betablockers, calcium channel blockers, loop diuretics, thiazides, mineralocorticoid receptor antagonists, antiplatelets, anticoagulants

6.2. For randomisation

6.2.1. Inclusion criteria

1. Age 18 years to <85 years.
2. Type 1 diabetes.
3. Insulin dose ≥ 0.5 units/kg body weight at screening **or** BMI ≥ 25 kg/m² at screening
4. Using continuous glucose monitor at screening or willing to use one for the duration of the trial.
5. Diagnosis of heart failure (HF) or high-risk for HF, defined as any of the following:
 - NT-proBNP ≥ 250 ng/L for those in atrial fibrillation/flutter, ≥ 125 ng/L for those in all other rhythms

or

Previous HF hospitalisation where HF was documented as the primary cause of hospitalisation and there was a requirement for loop diuretics

or

Impaired left ventricular (LV) function (i.e. LVEF <50% by any imaging modality) at any time

or

Preserved LV systolic function (LVEF $\geq 50\%$) with left atrial enlargement (2-dimensional measurement of left atrial width ≥ 3.8 cm or left atrial length ≥ 5.0 cm or left atrial area ≥ 20 cm² or left atrial volume index > 29 ml/m²) within the last 24 months.

or

Preserved LV systolic function (LVEF $\geq 50\%$) with left ventricular hypertrophy (2-dimensional measurement of end-diastolic interventricular septal diameter ≥ 1.2 cm or end-diastolic left ventricular posterior wall diameter ≥ 1.2 cm) within the last 24 months.

or

Preserved LV systolic function (LVEF $\geq 50\%$) with diastolic dysfunction (septal e' <7 cm/sec or lateral e' <10 cm/sec or average E/e' ≥ 15) within the last 24 months.

6. New York Heart Association Class II-IV at screening.
7. Kansas City Cardiomyopathy clinical summary score <85 at screening.

